5.7.1. Multiple Assessments for the Same Assessment Time Point

In the case of multiple observations (e.g., scheduled vs. unscheduled) at a specific visit, the first non-missing measurement will be used for analysis, unless multiple study assessments are expected (e.g., pre-dose vs. post-dose). When multiple study assessments are expected (e.g. ECG), the average of the replicate measurements should be

Pfizer Inc. / Protocol: C4971002 (TTI-622-02) IQVIA Biotech (Confidential) Project # ZZA82397

determined after the derivation of the individual parameter at same time point.

5.8. Software Version

All statistical analyses will be conducted using SAS® version 9.4 or higher (SAS Institute, Inc., Cary, North Carolina).

Non-compartmental Pk parameter calculations will be performed using Phoenix® WinNonlin® 8.3 or higher (Certara, Princeton, New Jersey). Graphics may be prepared using the same versions of SAS®, and/or Phoenix WinNonlin).

6. SUBJECT ACCOUNTABILITY

6.1. Subject Characteristics

Subject characteristics will be summarized by phase (dose escalation and expansion phase) and by dose cohort, based on the SAS, which consist of all participants who received at least one dose of study treatment.

6.1.1. Demography

Data collected about the following subject characteristics at the screening visit will be summarized:

- Age (in years). Age will be calculated as the number of years elapsed between birth date and the
 date of the screening visit.
- Age strata:
 - < 65 years
 - >= 65 years
 - o 65 74 years
 - o 75 84 years
 - ≥ 85 years
- Sex
- Race. If more than one race selected, summarize race as multiple.
- Ethnicity
- Height
- Weight
- BSA
- ECOG
- Number of prior regimens (1 vs 2, 3 or 4)
- Disease stage

Pfizer Inc. / Protocol: C4971002 (TTI-622-02) IQVIA Biotech (Confidential) Project # ZZA82397

6.1.2. Medical History

Medical histories will be summarized as the numbers and percentages of subjects with histories significant for each of the medical-history elements recorded on the Medical History (MH) CRF form. Coding will be performed using Medical Dictionary for Regulatory Activities (MedDRA), latest version. System Organ Class (SOC) and Preferred Term (PT) will be summarized by number and percentage of participants having at least one occurrence of a disease. All MH information, including diagnosis and start/end date will be listed for the SAS.

6.1.3. Cancer History

Cancer histories will be summarized as the numbers and percentages of subjects with significant medical-history elements recorded on the Disease History CRF form. Disease History information, including histology information, stages, disease site and progressive disease date will be listed.

6.1.4. Prior Surgeries

Prior surgeries for the current diagnosis will be summarized in a table organized to display the type of surgery, displaying counts and percentages of participants who reported at least one surgery in each group, by SOC and PT according to the MedDRA current version.

6.1.5. Prior Anti-cancer Treatments

Prior treatment for the current cancer diagnosis will be captured in the eCRF form 'Prior Treatments for Disease Under Study Diagnosis' and will be coded using WHO Drug Dictionary (WHO-DD) current version. A summary table will be organized to display the therapeutic subgroup and preferred names of each coded medication. The summary table will display counts and percentages of participants who reported using at least one medication in each represented therapeutic subgroup and preferred term. All information recorded in the CRF, including start/end date, best response for that regime, and reason for discontinuation, will be listed.

6.1.6. Concomitant Medications

Concomitant medication (CM) is defined as any medication with a start date prior to the date of the first dose of study treatment (before baseline) and continuing after the first dose of study treatment or with a start date between the dates of the first and last dose of study treatment. Any medication with a start date after the date of the last dose of study treatment will not be considered a CM. Any medication with a stop date prior to the first dose of study treatment (baseline) is defined as a prior treatment.

CM will be coded using the WHO-DD current version and will be summarized by the anatomical main class (1st level) of each coded medication and, within that, pharmacological subgroup (3rd level) of the coded medication. Participants are counted only once in each therapeutic class category. Concomitant medication will be summarized using the SAS

Template No.: NVA_TP_CR694 Revision 4 Reference: SOPCR008, WPCR013 Template Effective Date:15Feb2023 Page 19 of 46

Pfizer Inc. / Protocol: C4971002 (TTI-622-02) IQVIA Biotech (Confidential) Project # ZZA82397

and be tabulated for each dose level using frequencies and percentages. Percentages will be based on the number of participants in each dose level. A listing will be produced displaying the CM indication, dose, units, frequency, route, start/end date of the medication.

6.1.7. Concomitant Procedures

Concomitant procedure is defined as any procedure with a start date prior to the date of the first dose of study treatment (before baseline) and continuing after the first dose of study treatment or with a start date between the dates of the first and last dose of study treatment. Any procedure with a start date after the date of the last dose of study treatment will not be considered a concomitant procedure. Any procedure with a stop date prior to the first dose of study treatment is defined as a prior procedure.

Concomitant procedure will be coded using the MedDRA current version. SOC and PT will be summarized by number and percentage of participants having at least one occurrence of a concomitant procedure. A listing will be provided to display the procedure reason, location, and date.

6.2. Disposition

Counts and percentages will be calculated using the number of participants in SAS in the relevant cohort as the denominator. Screen failure is defined as a participant who signs informed consent but does not qualify for enrollment into the study. Screen failures and reasons will be reported on screen log and be summarized for all participants who sign informed consent.

For SAS, a summary of subjects will display the numbers and percentages of participants in each dose level by phase, total for escalation group, total for expansion group, and total for patients from escalation and expansion groups treated at the dose used in expansion.

End of Treatment (EOT) form will record the subject's status (completed or discontinued treatment), as well as the reason for discontinuation of each study drug (PLD and PF-07901801 are on separated forms) based on SAS.

End of Study (EOS) form will record participants who permanently discontinued the study, as well as the reasons, based on SAS.

6.3. Protocol Deviations

A listing will identify subjects who were enrolled even though they did not meet one or more eligibility criteria, or any other situations that were not compliant with the protocol. This data will be classified as major or minor deviation by the clinical team, that will review periodically the protocol deviations and finalize the deviations prior to the database lock and efficacy analyses.

Template No.: NVA_TP_CR694 Revision 4 Reference: SOPCR008, WPCR013 Template Effective Date:15Feb2023 Page 20 of 46

Pfizer Inc. / Protocol: C4971002 (TTI-622-02) IQVIA Biotech (Confidential) Project # ZZA82397

7. EFFICACY ANALYSES

Efficacy analyses will use data from the SAS (for all efficacy endpoints). For reporting response rate prior to study completion, the analysis population will include all patients with a baseline disease assessment, a follow-up assessment at least 4 weeks after the first dose and participants who have discontinued the study for any reason. Efficacy analyses will be descriptive in nature. Summary tables and figures will be presented by dose cohorts within the dose escalation and expansion phases, and combined, as applicable.

7.1. Efficacy Outcomes

For the efficacy endpoint, the clinical anti-tumor efficacy of PF-07901801 in combination with PLD will be evaluated by tumor response as assessed by the investigators using RECIST v1.1, according to protocol appendix B (Eisenhauer, 2009).

The response categories of target lesions and its definitions are described below:

Complete Response (CR)	Disappearance of all target lesions. Any pathological lymph nodes (whether target or non-target) must have reduction in short axis to < 10 mm.
Partial Response (PR)	At least a 30% decrease in the sum of the longest diameter (LD) of target lesions, taking as reference the baseline sum LD.
Stable Disease (SD)	Neither sufficient shrinkage to qualify for partial response nor sufficient increase to qualify for PD, taking as reference the smallest sum LD since the treatment started.
Progressive Disease (PD)	At least a 20% increase in the sum of the LD of target lesions, taking as reference the smallest sum on study (this includes the baseline sum if that is the smallest on study). In addition to the relative increase of 20%, the sum must also demonstrate an absolute increase of at least 5 mm. The appearance of one or more new lesions is also considered PD.
Not Evaluable (NE)	No imaging/measurement is done at all at a particular time point. If only a subset of lesion measurements is made at an assessment, usually the case is also considered NE at that time point, unless a convincing argument can be made that the contribution of the individual missing lesion(s) would not change the assigned time point response, which is most likely to occur in the case of PD.

The response categories of non-target lesions and its definitions are described below:

Complete Response (CR)	Disappearance of all non-target lesions and normalization of tumor marker level.
Stable Disease/	Persistence of one or more non-target lesion(s) or/and maintenance of tumor marker
Incomplete Response	level above the normal limits.
(Non-CR/Non-PD)	
Progressive Disease (PD)	Appearance of one or more new lesions and/or unequivocal progression of existing
	non-target lesions.

The tumor responses are required to be confirmed by radiographic tumor assessments. If an initial CR or PR is noted, confirmatory scans must be performed at least 4 weeks later. In the case of SD, follow-up measurements must have met the SD criteria at least once after study entry at a minimum interval of no less than 4 weeks.

Template No.: NVA_TP_CR694 Revision 4 Reference: SOPCR008, WPCR013 Template Effective Date:15Feb2023 Page 21 of 46

Pfizer Inc. / Protocol: C4971002 (TTI-622-02) IQVIA Biotech (Confidential) Project # ZZA82397

The table below summarizes how the overall response will be calculated at each timepoint based on target and nontarget lesion assessment:

Target Lesions	Non-target Lesions	New Lesions	Overall Response
CR	CR	No	CR
CR	Non-CR/non-PD	No	PR
CR	Not Evaluated	No	PR
PR	Non-PD or not evaluated	No	PR
SD	Non-PD or not evaluated	No	SD
Not Evaluated	Non-PD	No	NE
PD	Any	Yes or No	PD
Any	Any PD		PD
Any	Any Any		PD

Objective Response Rate (ORR) is defined as the percentage of participants in the treatment group who have a confirmed CR or PR to the treatment within the study period. The ORR will be summarized taking all target lesion, non-target lesion, and new lesion, into consideration.

The table below summarizes the overall response algorithm based on non-target lesion assessment only:

Non-target Lesions	New Lesions	Overall Response
CR	No	CR a
Non-CR/non-PD	No	Non-CR/non-PD
Not all evaluated	No	NE
Unequivocal PD	Any	PD
Any	Yes	PD

^a Best Response for this category also requires normalization of tumor markers, tumor nodes < 10 mm.

Best Overall Response (BOR) is defined as the best response recorded (CR, PR, SD, PD, NE per RECIST) from the start of the treatment until disease progression, recurrence, start of new anti-cancer therapy or death, whichever is earlier, taking as reference for PD the smallest measurements recorded since the treatment started. The participant's best response assignment will depend on the achievement of both measurement and confirmation criteria. The evaluation of BOR will be determined according to the table below when confirmation of CR and PR is required:

Overall Response (OR)		Book Owner II Book on a CROP)	
First Timepoint	Subsequent Timepoint	Best Overall Response (BOR)	
CR	CR	CR	
CR	PR	SD, PD or PR a	

Pfizer Inc. / Protocol: C4971002 (TTI-622-02) IQVIA Biotech (Confidential) Project # ZZA82397

		SD provided minimum criteria for
CR	SD	SD duration met (≥4 weeks),
		otherwise, PD
		SD provided minimum criteria for
CR	PD	SD duration met (≥4 weeks),
		otherwise, PD
		SD provided minimum criteria for
CR	NE	SD duration met (≥4 weeks),
		otherwise, NE
PR	CR	PR
PR	PR	PR
PR	SD	SD
		SD provided minimum criteria for
PR	PD	SD duration met (≥4 weeks),
		otherwise, PD
		SD provided minimum criteria for
PR	NE	SD duration met (≥4 weeks),
		otherwise, NE
NE	NE	NE

^a If a CR is truly met at first timepoint, then any disease seen at a subsequent timepoint, even disease meeting PR criteria relative to baseline, makes this disease PD at that point (since disease must have reappeared after CR). Best response would depend on whether minimum duration for SD was met. However sometimes 'CR' may be claimed when subsequent scans suggest small lesions were likely still present and in fact the participant had PR, not CR at the first time point. Under these circumstances, the original CR should be changed to PR and the best response is PR.

For participants with asymptomatic progression and in the absence of unacceptable toxicity, the participant should continue treatment and a confirmation scan should be conducted at least four weeks later to document objective progression prior to removing the participant from study treatment.

7.1.1. Primary Efficacy Outcome Analysis

Objective Response Rate (ORR), defined as the proportion of participants' best overall response achieving a confirmed CR or PR, per investigator, at any time on the study, will be summarized descriptively by dose cohort within the dose escalation and expansion phases. Baseline documentation of "target" and "non-target" lesions (lesion count and maximum lesion length) will be recorded in listings. The sum of diameters will be calculated for all target lesions at baseline and at each subsequent tumor assessment as a measure of tumor burden. The baseline lesion size or the smallest measurement on study value will be used as reference by which to characterize the lesion response.

Per RECIST criteria, target lesions considered 'too small to measure' will be assigned a default value of 5 mm and

Pfizer Inc. / Protocol: C4971002 (TTI-622-02) IQVIA Biotech (Confidential) Project # ZZA82397

those identified as 'not present' will be assigned 0 mm for purposes of analysis.

For efficacy response parameters, a 95% confidence interval (CI) using Wilson's score method will be presented for the phase 2 expansion cohorts, or combined data from phase 1 and phase 2 at the common dose used in the expansion cohort. All SAS participants will be included in the denominators for percentage, even if the participant had a NE response. The Objective Response Rate and BOR (CR, PR, SD, PD, NE) will be summarized descriptively for RECIST assessment method, for both phase 1 dose escalation and phase 2 expansion cohorts, and combined for the common dose.

Similarly, the proportion of participants with a BOR as CR and the proportion of participants with a BOR as PR at any time during the study will be summarized as part of the BOR.

Overall tumor response assessment data will be presented in listings.

7.1.2. Secondary Efficacy Outcome Analysis

Duration of response (DOR) will be calculated for participants who achieve a confirmed CR or confirmed PR, and is defined as the time from the date of first documented response (CR or PR) to the date of documented progression or death of any cause after achieving response. Participants who complete or discontinue the study without disease progression or death, as well as participants who receive alternate anti-cancer therapy prior to disease progression, will be censored at their last adequate response assessment date or last adequate assessment prior to the start date of alternate anti-cancer therapy. The number of events and the number of censored participants will be summarized, and the median time to PD or death event (reported in days), its 95% confidence interval (using Brookmeyer-Crowley method), and the 25th and 75th percentiles on the time to event for cohort will be summarized.

Disease Control Rate (DCR) is defined as the percentage of participants who have achieved CR, PR, or SD lasting at least 12 weeks. DCR at any time during the study will be summarized, as per the RECIST assessment method.

Progression Free Survival (PFS) is defined as the time from the first PF-07901801 injection (Cycle 1 Day 1) to PD or death of any cause, whichever is first. Participants who complete or discontinue the study without disease progression or death, as well as participants who receive alternate anti-cancer therapy prior to disease progression, will be censored at their last adequate response assessment date or last adequate assessment prior to the start date of alternate anti-cancer therapy. If date of progression occurs on the same date as the start of new anticancer therapy, the progression will be counted as an event. If there is PD or death after missing 2 planned assessments, the participant will be censored at the last non-PD assessment. Censoring reasons will be summarized in the PFS output.

For participants who do not have an adequate baseline tumor assessment or who do not have any postbaseline tumor assessments, censoring will occur on the date of first dose unless death occurred on or before the time of the second planned tumor assessment in which case the death will be considered an event. Note for participants who died without

Template No.: NVA_TP_CR694 Revision 4 Reference: SOPCR008, WPCR013

Template Effective Date:15Feb2023

Pfizer Inc. / Protocol: C4971002 (TTI-622-02) IQVIA Biotech (Confidential) Project # ZZA82397

any post baseline assessments and meet the definition of 2 or more missing assessment, the reason for censoring will be documented as 2 or more missed assessments and censoring will occur on the date of first dose.

The number of events and the number of censored participants will be summarized. PFS rate at selected times, as well as the median time to event (reported in days), its 95% confidence interval (using Brookmeyer-Crowley method), and the 25th and 75th percentiles on the time to event for cohort will be summarized. Kaplan-Meier plot of PFS will also be provided.

Overall Survival (OS) is defined as the time from the first PF-07901801 injection (Cycle 1 Day 1) to death of any cause. Participants without death date at the time of analysis will be censored at their last known alive date. Kaplan-Meier methodology similar to the PFS analysis will be used to summarize the results.

Waterfall plot for target lesion tumor response by individual will be presented, indicating best tumor response (maximum reduction of the sum of longest diameters from baseline) at any time point for each subject. The plot will have one bar per subject sorted from worst to best response with color by dose administered. Tumor response will be calculated based on the type of cancer that the participant has, with the appropriate measure using RECIST.

Spaghetti plots for target lesion tumor response by time will be presented for all participants at all visits, by dose. One line will be drawn per subject with color by response type. The horizontal axis will be the time and the vertical axis will be the percent change from baseline in tumor response. One set of spaghetti plots will be generated for RECIST assessment and only participants with non-missing tumor assessments will be shown.

Swimmer plots for tumor response will be generated with RECIST assessment. The plots will have one horizontal bar per subject firstly sorted by Best Response, and then sorted from earliest to latest time to start of response for CR and PR; within categories of SD, PD and NE, participants will be sorted by maximum observation duration. Symbols within the swimmer plot will indicate time to start and end of each new level of response (if the end of one response is the start of a new type of response by definition, only the start will be shown). The plots will also show the length of treatment duration a participant had.

8. SAFETY ANALYSES

Summary of AEs and other safety parameters will be based on the safety analysis set (SAS) by phase and dose cohort, except for the DLT, which will be based on DLT-Evaluable Population (DLP) by dose cohort.

8.1.Exposure

On Day 1 of each cycle, PLD will precede administration of PF-07901801. An observation period between completion of PLD infusion and initiation of PF-07901801 infusion is not mandated. Cohorts/dose levels for phase 1 escalation

Template No.: NVA_TP_CR694 Revision 4 Reference: SOPCR008, WPCR013 Template Effective Date:15Feb2023 Page 25 of 46

Pfizer Inc. / Protocol: C4971002 (TTI-622-02) IQVIA Biotech (Confidential) Project # ZZA82397

part of the study with the intravenous exposure to study drugs PLD and PF-07901801 (after PLD) and its schedule of administration per 28-day cycle is summarized below:

Cohort / Dose Level (DL)	PLD Dose [mg/m²] Schedule of administration	PF-07901801 Dose [mg/kg] Schedule of administration
1	40 Day 1 of every 28 day-cycle	12 Cycle 1: Day 1, Day 8, Day 15, and Day 22 Cycle 2 and above: Day 1 and Day 15
2	40 Day 1 of every 28 day-cycle	24 Cycle 1: Day 1, Day 8, Day 15, and Day 22 Cycle 2 and above: Day 1 and Day 15
3	40 Day 1 of every 28 day-cycle	48 Any cycle: Day 1 and Day 15 ^a

The following rules apply during dose escalation:

- Starting dose at dose level 1 is 12 mg/kg.
- At least 3 participants will be enrolled at each dose level. When all participants at a dose level
 complete DLT assessments, the study will escalate to the next dose level and another 3 participants
 will be recruited in this order until MTD/RP2D.
- If agreed upon by the investigators and Pfizer (eg, based on safety, incidence of DLT, PK and dose-exposure data from prior and current cohorts) that increasing the dose further may not yield additional benefit, the dose may stay at the current dose level, be de-escalated to any dose, or no future escalation may be made, even if the dose escalation rule indicates to escalate.
- The need for dose escalation to a specific dose beyond 48 mg/kg or de-escalation to an intermediate
 dose level will be evaluated jointly by investigators and Pfizer based on cumulative clinical safety,
 PK, and preliminary efficacy data.

A participant who completes at least four cycles of treatment with PF-07901801 in combination with PLD and requires discontinuation of PLD due to PLD-related toxicity and who is receiving disease control may continue on study receiving PF-07901801 monotherapy beginning with the next cycle provided the participant has not experienced disease progression and PF-07901801 re-treatment guidelines as described in Section 9.1.2 of the protocol are met.

Exposure to PF-07901801 and PLD will be summarized with descriptive statistics for the number of non-zero doses received, duration of dosing (weeks), total cumulative dose (mg/kg for PF-07901801, mg/m² for PLD), and overall relative intensity.

Duration of treatment is defined as the time (in weeks) from first dose of study drug in cycle 1 to the last dose of study drug in the last cycle a participant had.

Total cumulative dose is the sum of the actual doses of PF-07901801 or PLD received.

Pfizer Inc. / Protocol: C4971002 (TTI-622-02) IQVIA Biotech (Confidential) Project # ZZA82397

The calculation algorithm for duration of exposure (in weeks) for each drug and intended duration of PF-07901801 treatment will be:

- Duration of PLD exposure (weeks) = (Last PLD dose date first PLD dose date + 28) / 7
- Duration of PF-07901801 exposure (weeks)
 - DL1 and DL2 → If the last dose occurs during cycle 1: (Last PF-07901801 dose date first PF-07901801 dose date + 7) / 7
 - DL1 and DL2 → If the last dose occurs during cycle 2 and beyond: (Last PF-07901801 dose date – first PF-07901801 dose date + 14) / 7
 - DL3: (Last PF-07901801 dose date first PF-07901801 dose date + 14) / 7

Overall relative intensity (in %) for each drug is calculated as 100 × cumulative dose received divided by cumulative dose planned, where:

- Cumulative dose of PLD planned (mg/m²) = Planned PLD dose/cycle (40) × Duration of PLD exposure (weeks)
- Cumulative dose of PLD received (mg/m²) = Sum of all PLD doses (mg/m²) actually received.
- Relative Dose Intensity (%) of PLD = Cumulative dose of PLD planned (mg/m²) / Cumulative dose
 of PLD received (mg/m²) × 100%
- Cumulative dose of PF-07901801 planned (mg/kg), where D = planned dose for the participants according to the DL (12, 24 or 48 mg/kg) and C = number of treatment cycles:
 - DL1 and DL2: (planned PF-07901801 dose/cycle × cycle 1 × number of planned administrations of PF-07901801 in cycle 1) + (planned PF-07901801 dose/cycle × number of cycles of PF-07901801 after cycle 1 × number of planned administrations of PF-07901801 per cycle) = (D × 1 × 4) + (D × [C-1] × 2)
 - DL3: planned dose/cycle × number of cycles of PF-07901801 × number of planned administrations of PF-07901801 per cycle = 48 × C × 2
- Cumulative dose of PF-07901801 received (mg/kg) = Sum of all PF-07901801 doses (mg/kg) actually received.
- Relative Dose Intensity (%) of PF-07901801 = Cumulative dose of PF-07901801 planned (mg/m²)
 / Cumulative dose of PLD received (mg/m²) × 100%

The number of drug administrations with dose reduction, infusion held or permanently withdrawn will also be

Pfizer Inc. / Protocol: C4971002 (TTI-622-02) IQVIA Biotech (Confidential) Project # ZZA82397

summarized descriptively by cohort, for each study drug (PF-07901801 and PLD).

In addition, the planned dosing date and the actual dosing date will be listed. Listings will be provided with the information from all the study drug administration eCRFs. Reasons for missed doses of PF-07901801 and PLD will be listed.

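### SAP 8.1 defines relative dose intensity in two opposite ways, and neither, taken literally, gives a correct value for PLD

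*SAP*

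**What the plan says.** SAP 8.1 lists four exposure statistics to be summarized for each drug: number of non-zero doses, duration, and "total cumulative dose (mg/kg for PF-07901801, mg/m² for PLD), and overall relative intensity". The general definition is "Overall relative intensity (in %) for each drug is calculated as 100 × cumulative dose received divided by cumulative dose planned". The bullets beneath it are meant to supply the terms:

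- **Planned PLD:** "Cumulative dose of PLD planned (mg/m²) = Planned PLD dose/cycle (40) × Duration of PLD exposure", with that duration in weeks. The schedule table in the same section gives PLD as "40 Day 1 of every 28 day-cycle".
- **PLD relative intensity:** "Relative Dose Intensity (%) of PLD = Cumulative dose of PLD planned (mg/m²) / Cumulative dose" of PLD received, times 100%.
- **Planned PF-07901801**, in mg/kg, with D the planned dose and C the number of cycles: 4D + 2D(C − 1) at dose levels 1 and 2, and 48 × C × 2 at dose level 3.
- **Received PF-07901801:** "Cumulative dose of PF-07901801 received (mg/kg) = Sum of all PF-07901801 doses (mg/kg) actually received".
- **PF-07901801 relative intensity:** "Relative Dose Intensity (%) of PF-07901801 = Cumulative dose of PF-07901801 planned (mg/m²"), divided by "Cumulative dose of PLD received (mg/m²) × 100"%.

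SAP 1.2 and 1.3 contain no correction to any of this.

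**The concern.** The listed formulas depart from the general definition in three ways.

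1. Both ratios are upside down: planned over received instead of received over planned.
2. Planned PLD multiplies a per-cycle dose by a number of weeks. The SAP's own duration formula counts four weeks per cycle, so planned PLD is four times too large.
3. The PF-07901801 ratio has the wrong drug in its denominator and the wrong unit on its numerator. The right quantity, PF-07901801 received in mg/kg, is defined one bullet earlier and not used.

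The first two errors do not cancel. Restoring the general definition leaves PLD four-fold too low; following the bullets makes PLD intensity rise as less PLD is given. The PF-07901801 bullet responds to PLD reductions but not to how much PF-07901801 the participant received. Exposure fills SAP Tables 10 to 13, and Tables 12 and 13 are specifically for participants with dose reductions, where an inverted ratio misleads most.

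**Working it through.** The SAP states no numerical relative intensity, so there is no figure to reproduce. The check applies the SAP 8.1 formulas to simple dosing histories.

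**Inputs (all SAP 8.1).** PLD 40 mg/m² once per 28-day cycle. PLD duration in weeks = (last dose date − first dose date + 28)/7; the minus sign is missing in the text available to me and I treat it as lost in extraction. Planned PF-07901801 as given above.

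**PLD, four on-time cycles.** First to last dose is 84 days, so duration = (84 + 28)/7 = 16 weeks.

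- Planned as written: 40 × 16 = 640 mg/m².
- Planned by the schedule: 40 × 16/4 = 160 mg/m².

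| PLD received | Correct | General definition, planned as written | Listed formula |
|---|---|---|---|
| 160 mg/m² (full) | 160/160 = 100% | 160/640 = 25% | 640/160 = 400% |
| 120 mg/m² (every dose at 75%) | 120/160 = 75% | 120/640 = 18.75% | 640/120 = 533% |

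The 25% and 400% results are the same for 1, 2, 4, 6 or 12 full on-time cycles. If r is the correct intensity as a proportion (weeks/4 basis), the general definition returns r/4 and the listed formula returns 4/r. These equal r only at r = 0 and r = 2 (200%), so no plausible value is reported correctly. Repairing only the weeks factor and leaving the ratio inverted gives 160/120 = 133% for the participant at 75%, so reduced dosing would read as over-dosing.

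**PF-07901801, four cycles of both drugs.** Planned dose:

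- 12 mg/kg: 12 × 4 + 12 × 3 × 2 = 120 mg/kg
- 24 mg/kg: 24 × 4 + 24 × 3 × 2 = 240 mg/kg
- 48 mg/kg: 48 × 4 × 2 = 384 mg/kg

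| Dosing history | Correct | Listed formula at 12 / 24 / 48 mg/kg |
|---|---|---|
| Both drugs full (PLD received 160) | 100% | 75% / 150% / 240% |
| Half the PF-07901801 given, PLD full | 50% | 75% / 150% / 240% (unchanged) |
| PF-07901801 full, PLD at 75% (PLD received 120) | 100% | 100% / 200% / 320% |

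Under the general definition, with PF-07901801 in both places, full dosing gives 100% at every level on the default schedule.

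**Monotherapy after PLD.** SAP 8.1 lets a participant continue PF-07901801 alone after at least four combination cycles. Planned PF-07901801 then grows while PLD received stays fixed. At 24 mg/kg, four combination plus four monotherapy cycles, all given in full: planned = 24 × 4 + 24 × 7 × 2 = 432 mg/kg, and the listed formula returns 432/160 = 270%.

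**One 14-day delay, four full doses.** PLD duration = (98 + 28)/7 = 18 weeks.

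- Listed formula: 720/160 = 450%.
- General definition, planned as written: 160/720 = 22.2%.
- Corrected with weeks/4: 160/180 = 88.9%.
- Corrected with cycle counts: 160/160 = 100%.
- PF-07901801 planned dose is already cycle-based, so it gives 100%.

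**The case against.** The best reply is that the general definition governs and the bullets only supply its terms. Read that way, the inverted ratios and the PLD denominator in the PF-07901801 line are recognisable slips that a programmer would catch, and PF-07901801 comes out right. The planned-PLD line also has units that agree only if weeks are converted to cycles, and the schedule table gives the cycle length; with that conversion PLD is 160/160 = 100%.

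Some of this stands. The large percentages for PF-07901801 arise only if the bullets override the general definition. But the weeks-to-cycles conversion is written nowhere, so making it corrects the SAP rather than reads it, and it still requires a choice between weeks/4 and cycle counts, which differ under delay. The exact four-fold factor holds on the weeks/4 basis; on cycle counts the delay example gives 720/160 = 4.5-fold.

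It is also fair to say that the impact is low. Number of doses, duration and cumulative dose are summarized in their own right, SAP 8.2 derives delays, reductions and interruptions separately, and every administration is listed, so the statistic could be recomputed.

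**Conclusion.** The concern holds. As written, SAP 8.1 contradicts itself on the direction of the ratio, inflates planned PLD four-fold (weeks/4 basis), and uses the wrong drug and unit in the PF-07901801 line. At full on-time dosing PLD intensity is reported as 25% or 400% instead of 100%. PF-07901801 is correct under the general definition on the default schedule and wrong under its listed formula. Text extraction cannot explain this: the words for planned, received and the drug names are intact.

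The consequence is confined to descriptive exposure tables. No DLT, MTD, response-rate or six-of-25 decision depends on relative intensity. It should still be corrected, because the SAP says it governs the final analysis and following it literally puts a wrong PLD figure in the report whichever definition is programmed.

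**What to change.** Three edits are required in SAP 8.1:

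1. For each drug, relative intensity = 100 × cumulative dose received / cumulative dose planned, and delete the inverted versions.
2. Planned PLD = 40 × duration of PLD exposure in weeks/4, or 40 × number of PLD cycles. State which.
3. In the PF-07901801 line, use PF-07901801 received in the numerator and PF-07901801 planned in the denominator, both in mg/kg.

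Two further points are worth settling at the same time. Planned PF-07901801 is based on cycle counts and ignores delay; if PLD uses weeks/4, either put both drugs on one basis or footnote the difference. And if the optional Cycle 1 loading doses are used at dose level 3, the existing 48 × C × 2 expression would give 480/384 = 125% for four full cycles. The 4D + 2D(C − 1) expression should then apply to that cohort, unless the footnote marked on dose level 3 in the schedule table, whose text is missing from the copy available to me, already covers it.

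The cost is a few lines of SAP text and the matching derivation code. SAP 1.1 allows changes before database lock, and nothing changes at the sites.
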